6.2 Exclusion Criteria

Subjects are excluded from the study if any of the following criteria apply:

1. Requires more than 6 mL of product for optimal correction of both cheeks based on the Investigator's clinical judgment
2. Has undergone tissue augmentation with dermal fillers including HA, calcium hydroxylapatite, autologous fat, mesotherapy, or other cosmetic procedures (eg, face-lift, laser, photomodulation, intense pulsed light, radiofrequency, dermabrasion, chemical peel, or other ablative procedures) in the face within 12 months before screening or is planning to undergo any such treatment during the study

3. Has received any crosslinked HA filler in any anatomic area within 12 months of screening
4. Has undergone treatment with botulinum toxin in the cheek area (including crow's feet) within 6 months of screening or is planning to undergo such treatment during the study
5. Has ever received semipermanent fillers or permanent facial implants (eg, poly-L-lactic acid, polymethylmethacrylate, silicone, expanded polytetrafluoroethylene) anywhere in the face or is planning to be implanted with any of these products at any time during the study
6. Has facial tattoos, piercings, pigmentation, hair (ie, beard, mustache), or past trauma that would interfere with the visualization of the face for the effectiveness assessments
7. Has undergone a dental procedure within 6 weeks before treatment or plans to undergo a dental procedure (other than prophylaxis or dental fillings) during the course of the study
8. Has a tendency to develop hypertrophic scarring
9. Has a history of allergy to lidocaine, HA products, and/or to gram-positive bacterial proteins as HA is produced by *Streptococcus*-type bacteria, or is planning to undergo desensitization therapy during the term of the study
10. Has a history of anaphylactic shock
11. Has current cutaneous inflammatory or infectious processes (eg, acne, herpes), abscess, an unhealed wound, or a cancerous or precancerous lesion on the face (injection may be delayed to allow subjects with a history of recurrent oral herpes to take prophylactic antiviral/herpes medication for 2 days)
12. Is on an ongoing regimen of anticoagulation therapy (eg, warfarin) or is known to have a coagulation disorder
13. Is on an ongoing regimen of medications (eg, aspirin, ibuprofen) or other substances (eg, herbal supplements with garlic, ginkgo biloba, or ginseng) known to increase coagulation time within 10 days of undergoing study device injection (study device injection may be delayed as necessary to accommodate this 10-day washout period)
14. Has active autoimmune disease
15. Has received any investigational product within 30 days before enrollment or is planning to participate in another investigation during the course of this study
16. Has begun using any over-the-counter or prescription, oral or topical, anti-wrinkle products on the face within 30 days before enrollment or is planning to begin using such products during the study (subjects who have been on a regimen of such products for at least 30 days are eligible for the study if they intend to continue their regimen throughout the study)
17. Females who are pregnant, nursing, or planning a pregnancy during the study
18. Is an employee (or a relative of an employee) of the PI/EI/TI/site, Allergan, or representative of Allergan
19. Has a condition or is in a situation which, in the TI's opinion, may put the subject at significant risk, may confound the study results, or may interfere significantly with the subject's participation in the study

6.3 Life style Restrictions

Within the first 12 hours after treatment, it is recommended that subjects not apply make-up to the treatment area. Within the first 24 hours after treatment, it is recommended that subjects avoid shaving in the treatment area, strenuous exercise, extensive sun or heat exposure, and consumption of alcoholic beverages. Subjects will be advised not to enter a hot spring or sauna, or receive excessive exposure to the sun or temperatures below 0°C for 2 weeks following any study treatment (initial, touch-up, or repeat treatments). Exposure to any of these may cause temporary redness, swelling, and/or itching at the injection sites.

6.4 Screen Failures

Screen failures are defined as subjects who consent to participate in the clinical study but are not subsequently randomized/treated. A minimal set of screen failure information is required to ensure transparent reporting of screen failure subjects to meet the Consolidated Standards of Reporting Trials publishing requirements and to respond to queries from regulatory authorities. Minimal information includes demography, screen failure details, including reason for screen failure, eligibility criteria, and any SAEs.

Individuals who do not meet the criteria for participation in this study (screen failures) may not be rescreened except for those eligible for the Fitzpatrick V/VI safety cohort. Additional information on subject discontinuation/withdrawal criteria is provided in [Section 8](#).

7. Treatments

Study treatment is defined as any investigational treatment, marketed product, placebo, or medical device intended to be administered to a study subject according to the study protocol.

7.1 Treatments Administered

Study Treatment Name	JUVÉDERM VOLITE™ XC
Formulation	Injectable gel
Concentration	12 mg/mL HA + 0.3% lidocaine (w/w gel)
Route of Administration	Intradermal, 32 G 1/2" or 32 G 3/16" needle in multiple microdepot injections across both cheeks
Packaging and Labeling	
JUVÉDERM VOLITE XC will be provided sterile in plastic syringes. Each kit will contain 1 or more blisters, each containing 1 syringe prefilled to 1.0 mL and 2 single-use sterile needles (32 G 1/2"), specifically intended for injecting JUVÉDERM VOLITE XC. The 32 G 3/16" needles will be supplied separately. An investigational caution label, such as the following, will appear on the individual syringe package and the outer box:
 
Protocol 1867-701-008 Kit# VVVVV Lot# VVVV 'V CAUTION - Investigational Device. Limited by Federal (or United States) law to Investigational Use Use as directed per protocol

Manufacturer	Allergan Industrie, SAS
Number and Timing of Treatments	
 Initial treatment Day 30: optional touch-up Month 6: optional repeat treatment (treatment group only)
Volume Per Treatment	
 Initial treatment: up to 4 mL Optional touch-up treatment: up to 2 mL Optional repeat treatment: up to 4 mL

[figure not shown]
7.1.1 Instructions for Use and Administration

The TIs must be experienced in the use and administration of HA in injectable gels and be practicing in the field of aesthetic medicine, dermatology, or plastic/cosmetic/reconstructive surgery. Before the study begins, the TIs will receive training in the administration of JUVÉDERM VOLITE XC according to the technique specified for this study. This injection technique is multiple microdepot intradermal injections to the cheeks, from the zygomatic arch to the edge of the jaw, lateral from the nasolabial fold and oral commissures to the preauricular cheek (see allowable treatment area in [Figure 7-1](#)). Needle length selection, total injection volume, and injection spacing will be determined by the TI in accordance with the maximum volume restrictions of 4 mL for initial and repeat treatments and 2 mL for touch-up treatment. Topical anesthesia and/or ice may be applied prior to injection to relieve pain as directed by the TI. After ensuring that the subject has thoroughly washed the treatment area with soap and water,

the area must be prepped with alcohol or other antiseptic. The detailed injection technique guidelines are provided in the investigational DFU included in the Site Study Binder.

During each study visit, subjects will be required to remove all make-up, and male subjects must be clean-shaven in the treatment area to avoid interference with effectiveness assessments.

Figure 7-1 **Allowable Treatment Area**

7.1.2 Washout Intervals

Washout Intervals	Medication or Procedure
10 days before treatment	
 Ongoing regimen of medications and/or substances known to increase coagulation time (eg, aspirin, ibuprofen, or herbal supplements) 
NOTE: The 10-day washout period for anticoagulants must continue for 3 days after treatment (initial, touch-up, and repeat) is administered

30 days before enrollment	
 Any investigational product

7.1.3 Run-In Medications and Administration

Run-in Intervals	Medication
2 days before treatment	
• Prophylactic herpes treatment for subjects with a history of recurrent oral herpes lesions
30 days before enrollment	
• Over-the-counter or prescription, oral or topical, anti-wrinkle products on the face for subjects who will use such products during the study

7.1.4 Study Supplies

The sponsor will provide product kits, 32 G 3/16" needles, digital imaging equipment, mirrors for subject assessments, subject e-diaries, and subject questionnaires. The investigational site is responsible for routine supplies related to device administration and follow-up visits (eg, anti-septics, drapes, gloves, gauze, anesthesia, ice packs, urine pregnancy test kits (with sensitivity of at least 50 mIU/mL for human chorionic gonadotropin), blood pressure cuff, scale, and internet connection for IWRS and eCRF completion.

7.2 Treatment Modification

Retreatment Criteria

A subject may receive touch-up treatment if optimal correction has not been achieved at Day 30 in the opinion of the TI and is agreed upon by both subject and TI. The TI will have access to the EI-rated ACSS scores to assist in making the determination of whether optimal correction has been achieved. All treatment group subjects are eligible to receive repeat treatment at Month 6 if desired.

7.3 Concomitant Therapy

The use of concomitant medication, prescription or over-the-counter, as well as concomitant procedures or therapies is to be recorded on the subject's eCRF at each visit along with the reason for the treatment.

7.3.1 Prohibited Treatments

During the course of the study, subjects must not:

- Receive injectable anesthesia during study treatment
- Undergo tissue augmentation with dermal fillers including HA, calcium hydroxylapatite, autologous fat, mesotherapy, or other cosmetic procedures (eg, face-lift, laser,

photomodulation, intense pulsed light, radiofrequency, dermabrasion, chemical peel, or other ablative procedures) in the face

- Undergo treatment with botulinum toxin in the cheek area (including crow's feet)
- Undergo treatment with semipermanent fillers or permanent facial implants (eg, poly-L-lactic acid, polymethylmethacrylate, silicone, expanded polytetrafluoroethylene) anywhere in the face
- Undergo a dental procedure (other than prophylaxis or dental fillings)
- Be on a regimen of medications (eg, aspirin, ibuprofen) or other substances (eg, herbal supplements with garlic, ginkgo biloba, or ginseng) known to increase coagulation time for 3 days after each study treatment
- Receive any other investigational product
- Use any over-the-counter or prescription, oral or topical, anti-wrinkle products on the face that were not a stable regimen for at least 30 days prior to study enrollment
- The use of hyaluronidase for aesthetic purposes is not permitted. If hyaluronidase is used, the subject will be followed for safety only from that point on.

The decision to administer a prohibited medication/treatment during the study period is done with the safety of the study subject as the primary consideration. When possible, sponsor is to be notified before the prohibited medication/treatment is administered.

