8.1 Withdrawal from the Study

If a subject has a positive urine pregnancy test prior to initial treatment, the subject will be exited from the study. If the test is positive at the touch-up treatment visit, no touch-up treatment will be performed, but the subject will continue to be followed in the study and will be exited at Month 6. If the test is positive at the repeat treatment visit, no repeat treatment will be performed, and the subject will be exited from the study. Pregnancies for treated subjects will be followed as described in [Section 9.5.6](#).

In addition, a subject must be withdrawn from the study if he/she:

- Receives any dermal filler or fat injection to the cheeks
- Receives cosmetic procedures (eg, face-lift, laser, photomodulation, intense pulsed light, radiofrequency, dermabrasion, chemical peel, or other ablative procedures) in the face

A subject may withdraw from the study at any time at his/her own request or may be withdrawn at any time at the discretion of the PI/TI for safety, behavioral, or administrative reasons.

If the subject withdraws consent for disclosure of future information, the sponsor may retain and continue to use any data collected before such a withdrawal of consent.

If a subject withdraws from the study, he/she may request destruction of any samples taken and not tested, and the PI (or a delegated designee) must document this in the site study records.

See the schedule of activities ([Section 2](#)) for data to be collected at the time of study discontinuation and follow-up and for any further evaluations that need to be completed.

For any subject who withdraws from the study, the date and reason for withdrawal will be recorded on the eCRF. If an ISR or treatment-related AE is ongoing at the time of withdrawal, the TI will attempt to follow the subject until the ISR or AE has been resolved or follow-up is no longer possible. The PI/TI shall ask for the subject's permission to follow his/her status/condition outside the study.

If a subject fails to return for 1 or more scheduled study visits, the PI/TI (or designee) will attempt to contact the subject to determine and document the reason the subject has failed to return, and to encourage compliance with the study visit schedule.

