10.3.1.2 Primary Endpoint Analysis

The primary effectiveness variable is the EI's assessment of cheek skin smoothness on the ACSS. The primary effectiveness analysis is the ACSS responder rate at Month 1. A responder is defined as a subject who shows at least a 1-point improvement from baseline on the ACSS scale on both cheeks. The responder rate and corresponding 95% confidence interval will be summarized. A 2-sided, Fisher's exact test at the 5% level will be used to test whether the ACSS responder rate at Month 1 in the treatment group is significantly greater than that in the control group at Month 1 in the control period.

The primary effectiveness analysis will test for superiority of JUVÉDERM VOLITE XC treatment group over no treatment in the difference in ACSS responder rate based on the EI's assessment at Month 1. Month 1 refers to 1 month after the last treatment (initial or touch-up) for subjects in the JUVÉDERM VOLITE XC treatment group and 1 month after randomization for subjects in the no-treatment control group.

The null hypothesis is that the responder rate for the JUVÉDERM VOLITE XC treatment group is equal to the responder rate for the no-treatment control group. The alternative hypothesis is that the responder rates are not equal for the treatment group and the no-treatment control group. These hypotheses are stated as:

$$H_0: P_v - P_c = 0$$
$$H_a: P_v - P_c > 0 \text{ or } P_v - P_c < 0$$

where Pv and Pc denote the responder rates for the JUVÉDERM VOLITE XC group at Month 1 after last treatment (initial or touch-up) and for the no-treatment control group at Month 1 after randomization, respectively. Two-sided Fisher's exact test with 5% significance level will be used to compare treatment effects between JUVÉDERM VOLITE XC and the no-treatment control group. If the 2-sided p-value is less than 0.05 and the responder rate is greater for JUVÉDERM VOLITE XC than for the no-treatment control group, then JUVÉDERM VOLITE XC will be considered superior to the no-treatment control group.

For primary analysis, subjects with missing data at the primary timepoint (ie, Month 1) will be analyzed as non-responders. Details will be described in the SAP.

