5.3.2. Main Analytical Approach

The missing data in ACSS at Month 1 of CP will be imputed using the Multiple Imputation (MI) method for the mITT population as follows:

Step 1: The missing data will be imputed by cheek side and treatment group using the Fully Conditional Specification (FCS) method with seed = 820403 and nimpute = 30 based on the following model:

$$\text{Month 1 ACSS} = \beta_0 + \beta_1 \times \text{Age} + \beta_2 \times \text{Baseline ACSS}$$

Step 2: After imputation, the changes from baseline will be calculated, from which the responder status in ACSS at Month 1 of CP will be determined.

Step 3: Each complete dataset obtained from Steps 1 and 2 will be analyzed using SAS procedure FREQ

Step 4: The pooled results will be obtained using PROC MIANALYZE

The number and proportion of participants who achieved at least 1-point improvement from baseline at Month 1 of CP will be tabulated by treatment group. The aggregated responder rates by treatment group and the associated p-value and 95% CI estimated based on the normal approximation to assess the difference in the ACSS responder rate at Month 1 of CP between JUVÉDERM VOLITE XC and the no-treatment control will be presented. If the 2-sided p-value is less than 0.05, then the ACSS responder rate at Month 1 in JUVÉDERM VOLITE XC is statistically significantly different from that in the no-treatment control group during the control period. Furthermore, if the responder rate is greater for JUVÉDERM VOLITE XC than the no-treatment control group, then VOLITE will be considered superior to the no-treatment control group.

The detailed SAS codes are as follows:

```
proc mi data=adeff seed=820403 nimpute=30 out=mi;
  by trt01p cheek;
  class acss0 acss1;
  fcs logistic(/details);
  var age acss0 acss1;
run;
data lmi rmi; *separate imputed datasets by cheek side;
  set mi;
  if cheek='Left' then output lmi;
  if cheek='Right' then output rmi;
run;
data all; *obtain responder status variable;
  merge lmi rmi;
```

JUVÉDERM VOLITE™ XC

```
by _imputation_ subjid;
ldiff=lacss0-lacss1;
rdiff=racss0-racss1;
resp=0;
if ldiff >= 1 and rdiff>=1 then resp=1;
run;
ods output RiskDiffCol2=risk(where=(index(row,'Total')=0));
proc freq data=all;
  by _imputation_;
  tables trt01p*resp/riskdiff;
run;
proc sort data=risk; by row;
ods output VarianceInfo=Variance1;
ods output ParameterEstimates=Param1;
proc mianalyze data=risk;
  by row;
  modeleffects risk;
  stderr ase;
run;
```

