5.5. Other Effectiveness Endpoints Analysis

The other effectiveness endpoints listed in [Table 5-4](#) will be summarized descriptively based on the observed data.

The analyses of CP will be performed for the mITT population at Baseline and Month 1. The analyses of TP will be performed for the VT population at Baseline and Months 1, 2, 4, and 6.

JUVÉDERM VOLITE™ XC

The analyses of RP will be performed for the VRT population at Baseline and Months 1 and 4 post the repeat treatment.

The composite responder status is defined based on ACSS and FACE-Q Satisfaction with Skin Questionnaire overall converted score. A participant is counted as a composite responder if both criteria listed below are met:

- ACSS criterion: A participant with at least 1-point reduction from baseline in ACSS on both cheeks will be considered as an ACSS responder
- FACE-Q satisfaction with skin responder: A participant with change from baseline in FACE-Q overall converted score \geq half of standard deviation of FACE-Q overall converted score at baseline ([Pusic 2013](#))

Table 5-4 **Other Effectiveness Analyses**

Endpoint	Description	Analysis Period	Methodology
ACSS responder status as assessed by EI	Number (%) of responders by treatment group	TP, RP	Frequency counts and percentages
Raw value and change from baseline in ACSS	Summary by treatment group	CP, TP, RP	Continuous descriptive statistics
Raw value and change from baseline in FACE-Q Satisfaction with Skin questionnaire overall converted score	Summary by treatment group	TP, RP	Continuous descriptive statistics
Item score of FACE-Q Satisfaction with Skin questionnaire and aggregated categories of “satisfied” and “dissatisfied”	Number (%) of each response category by treatment for each of 12 individual items	CP, TP, RP	Frequency counts and percentages
AFLS responder status as assessed by EI	Number (%) of responders by treatment group	TP, RP	Frequency counts and percentages
Raw value and change from baseline in AFLS	Summary by treatment group	CP, TP, RP	Continuous descriptive statistics
Raw value and change from baseline in FACE-Q Appraisal of Lines questionnaire overall converted score (see Section 6.5.3 and Section 6.5.4)	Summary by treatment group	CP, TP, RP	Continuous descriptive statistics

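### Month 1 ACSS scores lost after hyaluronidase use, or after withdrawal for another facial procedure, are imputed as missing at random within arm, although the protocol counts missing subjects as non-responders

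*Protocol*

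**What the plan says.** Two protocol rules end effectiveness data collection after an intercurrent treatment.

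- Section 7.3.1, on hyaluronidase: "If hyaluronidase is used, the subject will be followed for safety only from that point on".
- Section 8.1: "In addition, a subject must be withdrawn from the study if he/she" meets either of two conditions: "Receives any dermal filler or fat injection to the cheeks", or "Receives cosmetic procedures (eg, face-lift, laser, photomodulation, intense pulsed light, radiofrequency, dermabrasion, chemical peel, or other ablative procedures) in the face".

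The two documents then treat a missing Month 1 ACSS score differently.

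- Protocol 10.3.1.2, for the primary analysis: "subjects with missing data at the primary timepoint (ie, Month 1) will be analyzed as non-responders". It leaves details to the SAP.
- SAP 5.3.2: "The missing data in ACSS at Month 1 of CP will be imputed using the Multiple Imputation (MI) method for the mITT population". The model is fitted separately for each cheek and arm: "The missing data will be imputed by cheek side and treatment group using the Fully Conditional Specification (FCS) method". Its only predictors are age and baseline ACSS. The reason for missingness plays no part.

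The SAP does not mention hyaluronidase and has no rule for the 8.1 procedure withdrawals. Its change list (SAP 6.2) covers changes from SAP version 1 only, so it does not explain the move away from the protocol's non-responder rule.

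For the Month 1 AFLS responder analysis, SAP 5.4.2 describes no handling of missing scores. The other effectiveness endpoints in SAP 5.5 "will be summarized descriptively based on the observed data".

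**The concern.** Imputation within arm assumes that a subject with a missing score would have responded like other subjects in that arm of the same age and baseline grade. That is hard to defend after hyaluronidase. The event that stops the rating also acts on the hyaluronic acid gel whose effect is being rated. The imputed score describes a subject who still has the product, while the actual subject may not. Only injected subjects have product to remove, so during the control period this error can arise only in the VOLITE arm, and it raises that arm's rate.

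The time at risk is also unequal. Month 1 counts from the last treatment, so a VOLITE subject who has a touch-up at Day 30 is exposed for about two months before the primary rating. A control subject is exposed for about one.

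What is at stake is the reported VOLITE responder rate and the difference from control, more than the significance of the test. At later visits the affected subjects leave the denominator without being counted anywhere.

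**Working it through.** **Plan's own figures.** With 112 and 56 subjects, rates of 80% and 40%, and a two-sided Fisher's exact test at 5%, exact enumeration gives 99.91% power (stated: 99.9%). For AFLS, 72 and 36 subjects at 80% and 45% give 94.4% (stated: 94.4%). Attrition: 168/0.8 = 210, which is 140 and 70 at 2:1. All reproduce.

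**Inputs.** 140 VOLITE and 70 control subjects; planned responder rates 80% and 40% (SAP 3). The number k of VOLITE subjects with such an event and no Month 1 score is not in the documents. I use k = 1 to 7 (0.7% to 5%) as an assumption.

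**Imputed response probability per affected VOLITE subject.** A responder must improve on both cheeks, but the cheeks are imputed separately. If m is the single-cheek response rate, the imputed both-cheek rate is about m².

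- Cheeks independent: m = √0.80 = 0.894, so m² = 0.80.
- Cheeks perfectly correlated: m = 0.80, so m² = 0.64.
- Simulation at a between-cheek correlation of 0.5 (binary response per cheek, no age or baseline effect): about 0.74.

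**Inflation relative to non-responder scoring** = k × (0.64 to 0.80)/140.

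- k = 1: 0.64/140 = 0.46 to 0.80/140 = 0.57 points.
- k = 3: 1.4 to 1.7 points.
- k = 7: 3.2 to 4.0 points.

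**Effect on the test.** With affected VOLITE subjects scored as non-responders, the VOLITE rate is 0.80 × (140 − k)/140. Power is for 140 against 70, with control at 40%.

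| k | VOLITE rate | Fisher power |
|---|---|---|
| 1 | 79.4% | 99.99% |
| 3 | 78.3% | 99.98% |
| 7 | 76.0% | 99.9% |
| 28 (all planned VOLITE attrition) | 64.0% | 88.8% |

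With control at 28/70, the expected result stays below p = 0.05 until k reaches 44 (77/140, p = 0.057).

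**Procedures in the control arm.** By the same arithmetic, one affected control subject imputed instead of scored as a non-responder raises the control rate by between 0.40²/70 = 0.23 and 0.40/70 = 0.57 points. The net effect on the difference therefore depends on how the procedures fall between arms.

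**Later visits, as an illustration.** Protocol 3.2 gives 34.9% response at Month 6 in the earlier European study. If 5 non-responders of 140 leave the table (an assumed count), 49/140 = 35.0% becomes 49/135 = 36.3%.

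**The case against.** The strongest reply is that the planned tipping-point analysis (SAP 5.3.3) already covers every combination of outcomes for the missing subjects, including all missing VOLITE subjects as non-responders. That stands as far as significance goes. However, the diagram displays p-values and gives no corrected responder rate, and it does not separate these subjects from ordinary dropouts. The other sensitivity analysis excludes anyone without a Month 1 rating.

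Second, the score is not always lost. SAP Table 6-2 accepts a rating from Day 2 to Day 46 after the last treatment, and Table 6-3 accepts one up to optional treatment or exit for controls. Protocol 8.1 refers to data collected at discontinuation. An exit ACSS inside the window would be used, so the point applies only where none exists.

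Third, procedures can occur in either arm. Scoring affected controls as non-responders lowers the control rate and so favours VOLITE. That is right, and it is why upward bias is asserted only for hyaluronidase.

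Two stronger readings are tempting. A reader might infer that treatment failures are being counted as successes. The documents do not say so: 7.3.1 bars hyaluronidase for aesthetic purposes and makes safety the main consideration when a prohibited treatment is given, and 8.1 does not link a facial procedure to a poor result. A reader might also infer that 7.3.1 and 8.1 contradict each other on follow-up. They set different consequences for different events, and 8.1 provides for attempts to follow ongoing injection site responses and treatment-related adverse events after withdrawal.

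**Conclusion.** The concern holds for Month 1 scores that are missing after these events. For hyaluronidase, the SAP's missing-at-random assumption is not credible, and the resulting bias in the VOLITE rate is upward. The figure of 0.57 points per subject is a ceiling, reached only if the cheeks respond independently. For other facial procedures the assumption is untested and the direction of bias in the treatment difference is open.

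The size rests on 140 VOLITE subjects, the planned 80% rate, an assumed event count, and the premise that hyaluronidase removes product. The documents do not spell out that premise, but it is consistent with the safety-only rule. A reader might go further and infer that the primary conclusion is at risk. At the planned rates it is not, for any plausible number of such events. The later-visit tables are descriptive, so how to score these subjects there is a choice of estimand; what is missing is a count of them.

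**What to change.** In SAP 5.3.2, add a step before imputation: where Month 1 ACSS is missing after hyaluronidase use, or after withdrawal under protocol 8.1 for filler, fat or a cosmetic procedure, set responder status to non-responder in both arms. Impute only the remaining missing scores. This agrees with protocol 10.3.1.2 for these subjects. The SAP should also state why it departs from that rule for the others.

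Apply the same step to the Month 1 AFLS responder analysis in SAP 5.4.2. Tabulate the affected subjects by arm and type of event. In the later-visit tables under SAP 5.5, report how many such subjects have left the denominator.

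The cost is a short SAP paragraph and a flag derived from concomitant medication, procedure and exit records, which the eCRF already collects. The downside is that the VOLITE responder rate may be slightly less favourable. No change to clinical management is proposed.
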